The Effect of Vitamin C-enriched Collagen Combined with Resistance Training on Muscle-tendon Unit Properties in Middle-aged Men and Women

Study protocol, statistical analysis plan and informed consent form.

Document date: 04/22/2024

1. Participant Flow

[figure not shown]

Figure 1. Flowchart of participant recruitment and intervention timeline (males).

[figure not shown]

Figure 2. Flowchart of participant recruitment and intervention timeline (females).

Study Protocol

Brief Summary:

The aim of this clinical trial is to investigate the longitudinal effects of hydrolyzed collagen ingestion combined with resistance training on muscle-tendon unit structure and function in middle-aged males and females.

The main research questions this clinical trial aims to answer are:

1. Does resistance training with hydrolyzed collagen ingestion lead to greater changes in tendon properties than resistance training alone in middle-aged health men and women?
2. Does resistance training with hydrolyzed collagen ingestion lead to greater changes in muscle size than resistance training alone?
3. Does resistance training with hydrolyzed collagen lead to greater increases in strength and power compared to resistance training alone in middle-aged, healthy men and women?

Participants will be randomly assigned to collagen or placebo groups. Participants will perform 24 sessions of high intensity resistance training across 12-weeks. Alongside each training session, participants will consume a beverage containing hydrolyzed collagen or maltodextrin, with both beverages containing vitamin C.

Researchers will compare the collagen and placebo groups to see if there would be beneficial effects on changes in muscle and tendon that are greater than resistance training alone. To achieve this, an dynamometry will be used to assess lower limb strength and ultrasound will be used to measure the morphological, mechanical, and material properties of the patellar tendon, as well the size and architecture of the vastus lateralis muscle.

Detailed Description:

Healthy, active, middle-aged men and women will ingest a beverage containing 30 g of hydrolyzed collagen with 50 mg of vitamin C or a calorie matched beverage (maltodextrin), also with 50 mg of vitamin C combined with high-volume, high-intensity resistance training for the lower body on 2 - 3 occasions per week for 8-12 weeks.

The aim of this study was to investigate the effect of combining hydrolyzed collagen with resistance training in middle-aged men and women. If supplementation with hydrolyzed collagen leads to a greater change in tendon size, stiffness, and Young's modulus than resistance training alone, this will allow us to recommend this type of intervention to young athletes seeking to improve tendon health and/or athletic performance. This is the first study to investigate the combination of hydrolyzed collagen supplementation with resistance training in middle-aged men and women. If supplementation with hydrolyzed leads to greater improvements in tendon size, stiffness, strength and/or power, this

will allow us to recommend this type of intervention to middle-aged athletes/trainees seeking to improve tendon health, reduce injury risk, or enhance athletic performance.

The experimental design of both arms will be the same, however Arm 1 will be health, middle-aged male participants and Arm 2 will be health, middle-aged female participants.

Arm/Group Information

Arm 1:

Training and nutrition intervention for middle-aged male participants (aged 35 - 59 years) who consumed hydrolyzed collagen (HC) or a placebo beverage with progressive resistance training.

Arm 1 Description:

This arm was designed as a double-blind, randomized control study with parallel groups. Middle-aged, recreationally trained men, pair-matched by age, body mass, height and baseline strength, were randomly allocated to the collagen (COL) or placebo (PLA) group.

During their initial laboratory visit, participants were screened and provided with a 3-day food diary and its completion instructions. Before undergoing baseline assessments, participants engaged in a warm-up routine that included 5 minutes of low-intensity jogging followed by 5 minutes of dynamic stretching. The baseline assessments of lower limb muscle-tendon unit properties, lower limb strength and power were conducted at the same time of day to mitigate any potential circadian effects.

The 12-week progressive lower-limb resistance training program comprised a combination of supervised and home-based training sessions focused on overloading the quadriceps femoris muscle-tendon unit. Training loads were adjusted weekly based on the prior session's performance using a linear progression model.

Each session was accompanied by the consumption of a flavor matched beverage. This beverage contained either 0 or 30 grams of hydrolyzed collagen (HC), combined with vitamin C. The 0 g beverage also contained vitamin C and was matched with the 30 g beverage for caloric content by the inclusion of maltodextrin.

Post-intervention, participants returned to the laboratory 72 hours after their final training session to repeat all baseline assessments.

Arm 2:

Training and nutrition intervention for middle-aged female participants (aged 35 - 59 years), who consumed hydrolyzed collagen (HC) or a placebo beverage with progressive resistance training.

Arm 2 Description:

This arm was identical to Arm 1 (male cohort), however it was conducted in middle-aged females.

1. Period

Arm 1: Participants were recruited from university staff, and sports and leisure clubs. Recruitment began in June 2021 and data collection was completed in December 2021.

Arm 2: Participants were recruited from university staff and sports clubs. Recruitment began in March 2023 and data collection was completed in June 2023.

2. Baseline Characteristics

Arm 1: 20 middle-aged males (mean \pm SD; age, 47 ± 5 years, body mass, 81 ± 12 kg; height 178 ± 7 cm)

Arm 2: 22 middle-aged females (mean \pm SD; age 37 ± 2 years, body mass, 69 ± 8 kg, 168 ± 4 cm)

- Age
 - > 35 and < 59 years;
- Sex
 - Male and female
- Ethnicity
 - Race and ethnicity information not collected
- Region of enrolment
 - Arm 1: Carlow, Ireland
 - Arm 2: Dublin, Ireland

3. Outcome measure information

Table 1. Outcome measures by study arm

	Number of participants analyzed	Description	Time frame
Primary	42 (Arm1: 20; Arm 2: 22)	m. vastus lateralis thickness (in millimeters)	Data analyzed between January 2022 & September 2023
Primary	43 (Arm1: 20; Arm 2: 22)	m. vastus lateralis fascicle pennation angle (in degrees)	Data analyzed between January 2022 & September 2023
Primary	43 (Arm1: 20; Arm 2: 22)	Patellar tendon cross sectional area (in squared millimeters) at 3 regions along the tendon length	Data analyzed between January 2022 & September 2023
Primary	43 (Arm1: 20; Arm 2: 22)	Bilateral vertical countermovement jump height (in centimeters)	Data analyzed between January 2022 & September 2023
Primary	Arm 1: 20	Patellar tendon stiffness (in Newtons per millimeter)	Data analyzed between January 2022 & September 2023

Primary	Arm 1: 20	Knee extensor maximal isometric torque (in Newton meters)	Data analyzed between January 2022 & September 2023
Primary	Arm 1: 20	Knee extensor rate of torque development (in Newton meters per second)	Data analyzed between January 2022 & September 2023
Primary	Arm 1: 20	Barbell back squat 10-repetition maximum (in kilograms)	Data analyzed between January 2022 & September 2023
Primary	Arm 1: 20	Bilateral horizontal broad jump distance (in centimeters)	Data analyzed between January 2022 & September 2023
Primary	Arm 2: 22	Lower limb maximal isometric force (in Newtons)	Data analyzed between July 2023 & September 2023
Primary	Arm 2: 22	Lower limb isometric rate of force development (in Newtons per second)	Data analyzed between July 2023 & September 2023
Primary	Arm 2: 22	20-metre sprint time (in seconds)	Data analyzed between July 2023 & September 2023

Statistical Analyses Plan (SAP)

In Arm 1, data from 20 male participants were analyzed and in Arm 2, data from 22 female participants were analyzed. The analyses of data collected from each arm were performed independently. All variables were ratio data, and normal distribution was assessed using the Shapiro-Wilk test, along with visual inspections of histograms, Q-Q plots, and box plots. All data met the assumptions of the parametric statistical analyses used in the study. Independent t-tests were used to assess differences between groups (COL, collagen and PLA, placebo) at baseline for all measures. The two-way analysis of variance (ANOVA) was performed on all measures taken at baseline and after the intervention to assess the main effects of group (COL vs PLA), time (pre- vs post- intervention), and any group \times time interactions. The only exceptions to this were for patellar tendon cross-sectional area, and rate of torque/force development. For the patellar tendon cross-sectional, a three-way ANOVA was used to assess main effect of location (along the length of the tendon), and any interactions between location, time (pre- to post- intervention) and group (COL vs PLA). Likewise for rate of torque/force development, a three-way ANOVA was used to assess main effect of time-window (0 – 50, 50 – 100, 100 – 150 ms after the onset of torque/force), time (pre- to post- intervention) and group (COL vs PLA) and any interactions between time-window, time and group. When significant main effects or interaction effects were observed, paired t-tests were used for post hoc pairwise comparisons. The level of statistical significance was set at $P < 0.05$

4. Adverse Event Information

During data collection period, any adverse event such as all-cause mortality or serious adverse event did not occur.

5. Certain Agreements

Are all PIs Employees of Sponsor? Yes

Results Disclosure Restriction on PI(s)?

No

6. Results Point of Contact

[name] Research Institute for Sport and Exercise Sciences, Liverpool John Moores

University [contact]; E-mail: [contact]

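### Do the total of 43 in three Table 1 rows and the lack of a combined men-and-women estimate call for a change to the analysis plan?

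*Combined protocol and SAP*

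**What the plan says.** In this document an arm is a sex cohort, and collagen and placebo are compared within each arm. Section 3, Table 1, lists 12 primary outcomes, of which four were measured in both cohorts. The vastus lateralis thickness row reports "42 (Arm1: 20; Arm 2: 22" as analysed. The rows for pennation angle, patellar tendon cross-sectional area and countermovement jump each report "43 (Arm1: 20; Arm 2: 22". The other eight rows belong to one cohort only: five show 20 for Arm 1 and three show 22 for Arm 2.

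The SAP states: "In Arm 1, data from 20 male participants were analyzed and in Arm 2, data from 22 female participants were analyzed". It continues: "The analyses of data collected from each arm were performed independently". It describes no estimate across the two cohorts.

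On design, the Arm 1 Description says "This arm was designed as a double-blind, randomized control study with parallel groups", with the men "pair-matched by age, body mass, height and baseline strength, were randomly allocated to the collagen (COL) or placebo (PLA) group". The Arm 2 Description adds: "This arm was identical to Arm 1 (male cohort), however it was conducted in middle-aged females". Research question 1 in the Brief Summary asks about "greater changes in tendon properties than resistance training alone in middle-aged health men and women", and question 3 on strength and power is framed the same way. Question 2, on muscle size, names no sex.

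**The concern.** Two things catch the eye. The first is that a number analysed for three primary outcomes contradicts the parts printed beside it. In principle this could mean that a participant was lost from one cohort's count, or that the analysis set differs between outcomes without explanation.

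The second is that questions 1 and 3 speak of men and women together, while the SAP delivers two separate small comparisons. For the four shared outcomes a reader gets two imprecise answers and no overall one. If one cohort reached significance and the other did not, the split could be misread as a sex difference. Since a total is printed for these four outcomes, one might also suppose that a combined analysis was intended and left out.

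**Working it through.** **The count**

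- Thickness row: 20 + 22 = 42, as printed. Reproduced.
- Pennation angle, tendon cross-sectional area and countermovement jump rows: 20 + 22 = 42, printed 43. Not reproduced; excess 43 − 42 = 1, or 1/42 = 2.4%.
- Other evidence: Section 2 (Baseline Characteristics) gives 20 males and 22 females; the eight single-cohort rows give 20 or 22; the SAP gives 20 and 22. Nothing readable supports 21 men or 23 women. The participant-flow figures were not available in the text reviewed.

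**What the slip could affect**

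The documents give neither group sizes nor an SD of change. Assume near-equal allocation, analysis of change scores, and units of a common SD. The half-width of the 95% interval for the collagen-minus-placebo difference is t × √(1/n₁ + 1/n₂).

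| Cohort | Split | SE | df | Half-width (SD) |
|---|---|---|---|---|
| 20 men | 10/10 | √(2/10) = 0.447 | 18 | 0.94 |
| 21 men | 10/11 | √(1/10 + 1/11) = 0.437 | 19 | 0.91 |
| 22 women | 11/11 | √(2/11) = 0.426 | 20 | 0.89 |
| 23 women | 11/12 | √(1/11 + 1/12) = 0.417 | 21 | 0.87 |

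So even the unsupported case of a 43rd participant moves a half-width by only 0.02 to 0.03 SD.

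**What a combined estimate would offer**

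Take cohort as a factor, with weights 1/(2/10) = 5 and 1/(2/11) = 5.5.

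- SE = √(1/10.5) = 0.309. With df 38 (t = 2.024) the half-width is 0.625 SD.
- If the women's SD is r times the men's, a pooled-variance ANOVA has residual variance (18 + 20r²)/38. At r = 0.67 this is 0.710, half-width 2.024 × √(0.710/10.5) = 0.53 men's SD. At r = 1.5 it is 1.658, half-width 2.024 × √(1.658/10.5) = 0.80.
- Power at a common true difference of 0.8 SD (two-sided 0.05, noncentral t): 0.395 men, 0.431 women, 0.71 combined.
- Chance that exactly one cohort is significant at 0.8 SD: 0.395 × (1 − 0.431) + 0.431 × (1 − 0.395) = 0.49.

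**What it would cost**

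- Effect of 0.8 SD in women only: the combined estimate targets 0.8 × 5.5/10.5 = 0.42 SD, power 26% against 43% in women alone.
- Effect of 0.8 SD in men only: 0.8 × 5/10.5 = 0.38 SD, power 23% against 40% in men alone.
- Difference in effect between cohorts: SE √(2/10 + 2/11) = 0.618, half-width 2.024 × 0.618 = 1.25 SD, too wide to be informative.
- Coverage: four of 12 outcomes and none of the strength outcomes. The isometric tests are in torque units for men and force units for women, and the 10-repetition squat was done in men only.
- Comparability: mean age 47 against 37 years, Carlow against Dublin, 2021 against 2023.
- Timing: Table 1 dates analysis of the shared outcomes from January 2022, and the women's recruitment began in March 2023. The men's results may have been known before the women's data existed.

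**The case for a change.** The best case for acting is this. The count error is certain: no rounding turns 20 + 22 into 43, and three identical rows make a text-extraction fault unlikely. It concerns primary outcomes and would look careless in a results report. A combined estimate needs no new data, and its interval would be about a third narrower (0.625 against 0.94 and 0.89 SD). The two cohorts have the same stated design, two research questions name both sexes, and the protocol foresees one recommendation for middle-aged athletes. Without a combined figure, a split result has about an even chance of arising at a common effect of 0.8 SD, and readers may over-interpret it.

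The arithmetic stands, and so does the caution about split results. The documents, however, propose no such inference, and no research question asks whether the sexes differ. Two cohort results also answer a question about men and women, and each cohort is a randomised comparison in its own right. The gain in precision assumes a common effect, which the documents neither state nor support; without it the combined figure dilutes a one-cohort effect.

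**Conclusion.** No change to the plan follows. The total of 43 is a clerical slip of one in three cells. The readable text points consistently to 42, and a look at source data would settle the small remaining doubt, since the flow figures could not be consulted. No test, estimate or sample-size statement uses the total. If an arm count were wrong instead, precision would shift by at most 0.03 SD, assuming near-equal allocation.

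Separate analysis by cohort is openly stated, respects the randomisation within each cohort, and suits a trial in which eight of 12 primary outcomes exist in one cohort only. A combined estimate trades a half-width of about 0.62 SD (0.53 to 0.80 men's SD if the cohorts' SDs differ by up to a factor of 1.5) against post hoc timing, partial coverage, unlike cohorts and dilution. Reasonable statisticians could choose either way, so its absence is not a defect. All figures in SD units rest on assumed 1:1 allocation and change-score analysis, and all but the 0.53 to 0.80 range on a common SD.

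### Do questions about men and women require an analysis over both arms, when 20 men and 22 women are analysed separately?

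*Combined protocol and SAP*

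**What the plan says.** Research question 1 in the Brief Summary asks whether collagen with training will "lead to greater changes in tendon properties than resistance training alone in middle-aged health men and women". Question 3 asks whether it will "lead to greater increases in strength and power compared to resistance training alone in middle-aged, healthy men and women". Question 2, on muscle size, names no sex. The same section says "Researchers will compare the collagen and placebo groups to see if there would be beneficial effects on changes in muscle and tendon". The Detailed Description makes "greater improvements in tendon size, stiffness, strength and/or power" the condition under which the authors would "recommend this type of intervention to middle-aged athletes/trainees seeking to improve tendon health", with no limit by sex.

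The Arm 1 Description says "This arm was designed as a double-blind, randomized control study with parallel groups". The Arm 2 Description adds "This arm was identical to Arm 1 (male cohort), however it was conducted in middle-aged females". The SAP then states "The analyses of data collected from each arm were performed independently". Its models contain group, time and, for two outcomes, tendon location or time-window. Arm is never a factor.

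Table 1 in section 3 lists 12 outcomes by study arm, all labelled Primary:

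- **Both arms (4):** vastus lateralis thickness, pennation angle, patellar tendon cross-sectional area (CSA), countermovement jump height.
- **Men only (5):** tendon stiffness, knee-extensor torque, rate of torque development, 10-repetition squat, broad jump.
- **Women only (3):** lower-limb isometric force, rate of force development, 20-metre sprint.

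**The concern.** The questions and the intended recommendation cover both sexes, but no analysis does. Two consequences seem to follow.

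First, each test rests on 20 or 22 people. If the true effect is the same in both sexes, chance alone will often make one arm significant and the other not. A reader could take that as benefit in one sex only. The SAP works by significance at 0.05, mentions no effect estimates or confidence intervals, and has no sentence warning against that reading.

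Second, stiffness is one of the gains that would support the recommendation, yet it is listed for men only. CSA is the only tendon property listed for women. Because the gains are joined by and/or, a stiffness gain in 20 men would meet the condition for advice that also reaches women. Calling Arm 2 identical to Arm 1 could hide the fact that 8 of the 12 outcomes belong to one arm only.

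The natural suggestion is an arm-stratified estimate for the four shared outcomes, with rules on the scope of conclusions.

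**Working it through.** **Inputs.** From the SAP: 20 men, 22 women, significance level 0.05. The documents give no allocation ratio, SD, effect size or power. Assumed: equal allocation (10/10 and 11/11), two-sided tests, pair matching ignored. Effects are in SD of change and, in steps 1 to 4, the SD is equal in both sexes.

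**The plan's own figure.** 20 + 22 = 42, as in the thickness row of Table 1. The other three shared rows print 43 beside the same 20 and 22, which is a clerical slip.

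**1. Precision.** Within an arm, SE = sqrt(1/n1 + 1/n2). The 95% half-width is the t quantile times SE.

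- Men: sqrt(2/10) = 0.447; × 2.101 (18 df) = 0.94 SD.
- Women: sqrt(2/11) = 0.426; × 2.086 (20 df) = 0.89 SD.
- Stratified: the weights 1/SE² are 5 and 5.5, so SE = 1/sqrt(10.5) = 0.309; × 2.023 (39 df) = 0.62 SD.
- Difference between arms: sqrt(2/10 + 2/11) = 0.618; × 2.024 (38 df) = 1.25 SD.

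**2. Power with a common effect (noncentral t).** Disagreement on significance is p1(1 − p2) + p2(1 − p1).

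| True effect | Men | Women | Stratified | Arms disagree |
|---|---|---|---|---|
| 0.5 SD | 18% | 20% | 35% | 31% |
| 0.8 SD | 40% | 43% | 71% | 49% |
| 1.0 SD | 56% | 61% | 88% | 49% |

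At 0.8 SD: 0.395 × 0.569 + 0.431 × 0.605 = 0.225 + 0.261 = 0.486. In simulation, the stratified interval excludes zero in 89% of those discordant trials. Splits of 8/12 and 9/13 barely alter this (38%, 42%, 70%; disagreement 48%).

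**3. Effect in one cohort only.** With 1.2 SD in men and zero in women, the stratified estimate averages 5 × 1.2/10.5 = 0.57. With the roles reversed it averages 5.5 × 1.2/10.5 = 0.63. In simulation:

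- The interval excludes zero in 40% and 47% of trials respectively.
- Among discordant trials it excludes zero in 52% and 58%.
- It covers the men's true effect in about 53% of trials and the women's in about 60%.

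So after a discordant result, a combined interval that excludes zero is more likely than not even when one sex gains nothing.

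**4. Can the data tell these cases apart?** Hardly. The group-by-arm test has 47% power for a difference of 1.2 SD and needs about 1.78 SD for 80%.

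**5. Unequal SD.** The change-score SDs are unknown. Section 2 shows wider baseline spread in men (body mass SD 12 against 8, height 7 against 4), which is only suggestive. Take a common raw effect of 0.8 of the women's SD. In simulation, men's SD at 1.5 times women's gives combined power of 52%, and the 89% in step 2 becomes 73%. At twice, combined power is 38% against 43% for women alone, and the 89% becomes 55%.

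**6. Multiplicity.** There are 4 × 2 + 5 + 3 = 16 arm-level analyses. If the combined interval is read as a test, the chance of at least one false positive rises from 1 − 0.95² = 9.8% to 11.7% per outcome. Over four independent outcomes it rises from 1 − 0.95⁸ = 34% to 1 − (1 − 0.117)⁴ = 39%.

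**The case for a change.** The best case for a change rests on the scope of conclusions and needs no statistical assumption. The recommendation has no limit by sex, stiffness was measured in men only, and the word identical does not fit the two outcome lists. Two sentences would settle it. On the shared outcomes, one small model would narrow the half-width from 0.94 and 0.89 to 0.62 SD and would discourage reading discordant p-values as a sex difference. It could be labelled post hoc and shown beside the arm results without a p-value.

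The facts in that case stand. Their force is limited for four reasons:

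- The questions can be read as asking about each sex, and for the shared outcomes the plan answers them that way. The sentence about comparing the groups does not promise a single comparison over both arms.
- The recommendation is a conditional statement of rationale, not an analysis rule. Table 1 marks stiffness as Arm 1 only, so its limit is visible. No passage reads a difference in significance as a sex difference.
- The gain from combining holds when effect and SD are similar in both cohorts. The documents cannot show that, and the interaction is too imprecise to check it. Recruitment was in Carlow in 2021 and Dublin in 2023, with mean ages 47 and 37. The Brief Summary and Detailed Description also give different accounts of training length and frequency, which must be reconciled before the cohorts are treated as interchangeable.
- The analysis is dated to September 2023 and the document to April 2024. A combined estimate added now could be chosen with the arm results known.

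**Conclusion.** No change to the plan follows. Separate analysis of two separately randomised cohorts is legitimate, and following the SAP as written gives sound arm-specific comparisons. A combined estimate is an optional post hoc extra with real costs. Under a common 0.8 SD effect and equal SDs it raises power from 40% and 43% to 71%. If only one cohort responds, it covers either cohort's true effect in only about 53% to 60% of trials, and if men's SD is twice women's it has less power than women alone. All these figures rest on assumed equal allocation and effects in SD units.

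What remains is reporting detail that a careful analyst would supply unprompted: single-arm results described as applying to the men or the women studied, and a difference in significance between arms not presented as a sex difference. Table 1 and the SAP already contain what is needed for that. The word identical, read against Table 1, can fairly be taken to describe the trial design and not the outcome list.

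### No model adjusts for the baseline value: the group × time test is valid, but baseline-adjusted ANCOVA would gain some power if the pre-post correlation is low to moderate

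*Combined protocol and SAP*

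**What the plan says.** The Statistical Analyses Plan gives one model for most outcomes: "The two-way analysis of variance (ANOVA) was performed on all measures taken at baseline and after the intervention", with group, time and their interaction. Tendon cross-sectional area and rate of torque/force development get a three-way ANOVA, with location or time-window as the third factor. Baseline values are also compared between groups by separate t-tests. No model has a baseline covariate. On pooling, "The analyses of data collected from each arm were performed independently".

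On allocation, the Arm 1 Description says participants were "pair-matched by age, body mass, height and baseline strength, were randomly allocated to the collagen (COL) or placebo (PLA) group". For Arm 2 there is only the statement "This arm was identical to Arm 1 (male cohort), however it was conducted in middle-aged females". No model has a term for the pair or for any matching variable.

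The Arm 1 Description also says "participants returned to the laboratory 72 hours after their final training session to repeat all baseline assessments", so each outcome's baseline value should already be on file.

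**The concern.** The research questions in the Brief Summary are all between-group: does collagen add to what training achieves alone? What matters is therefore the precision of the collagen-placebo contrast. A group × time test on two time points implicitly fixes the slope of post on baseline at 1. ANCOVA estimates that slope, and unless the pre-post correlation is high it gives a tighter estimate from the same data. With about 10 or 11 participants per group, a null interaction is hard to read if the test gives up precision that was available at almost no cost.

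**Working it through.** **Plan's own figure.** There is none to reproduce: the documents give no sample-size or power calculation.

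**Inputs from the documents.** N = 20 (Arm 1) and 22 (Arm 2), analysed separately; significance at 0.05. Table 1 yields 12 two-way analyses once tendon area and rate of torque/force development are set aside.
- Arm 1 has 7: muscle thickness, pennation angle, countermovement jump, tendon stiffness, isometric torque, squat and broad jump.
- Arm 2 has 5: muscle thickness, pennation angle, countermovement jump, isometric force and sprint.

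**Assumptions.** Equal groups (10 + 10 and 11 + 11; only totals are given), two-sided test, time within subject, normal data, equal pre and post SD s, true effect 0.75 SD, and pre-post correlation r from 0.5 to 0.9.

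**Step 1: variances.**
- Change score: residual variance 2s²(1 − r), N − 2 error df.
- ANCOVA: residual variance s²(1 − r²), N − 3 error df, with an average small-sample inflation of 1 + 1/(N − 4) for estimating the slope.
- Ratio, ANCOVA to change: (1 + r)/2 × [1 + 1/(N − 4)].

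For N = 20 the inflation is 1 + 1/16 = 1.0625. Without matching, the ratio is 0.75 × 1.0625 = 0.80 at r = 0.5, 0.85 × 1.0625 = 0.90 at 0.7, 0.90 × 1.0625 = 0.96 at 0.8 and 0.95 × 1.0625 = 1.01 at 0.9. Break-even is r = 2/1.0625 − 1 = 0.88. For N = 22 it is 2/(1 + 1/18) − 1 = 0.89.

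**Step 2: power.** Worked case, N = 20, r = 0.5, s = 1:
- Change-score standard error is √(1 × 2/10) = 0.447, so effect/SE = 0.75/0.447 = 1.68. Exact noncentral power is 35.5%.
- ANCOVA average standard error is √(0.75 × 1.0625 × 2/10) = 0.399, so effect/SE = 0.75/0.399 = 1.88.

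Simulated power, 100,000 trials per setting, no matching (a repeat simulation agreed within 1 point):

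| r | N = 20: change / ANCOVA | Gain (points) | N = 22: change / ANCOVA | Gain (points) |
|---|---|---|---|---|
| 0.5 | 35.3% / 42.5% | 7.2 | 38.6% / 46.7% | 8.1 |
| 0.7 | 53.3% / 57.6% | 4.3 | 58.1% / 62.8% | 4.7 |
| 0.8 | 70.7% / 72.5% | 1.8 | 75.4% / 77.3% | 1.9 |
| 0.9 | 94.2% / 93.9% | −0.3 | 96.3% / 96.1% | −0.2 |

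Under the null, both tests reject at about 5% in this unmatched setting.

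**Step 3: does the matching change this?** It depends on how the matching variables relate to the outcome. Take N = 20, r = 0.5, and pairs formed on a score correlated 0.7 with the outcome's baseline:
- If the score relates to the post value only through the outcome's baseline, the change-score test rejects a true null 3.8% of the time and ANCOVA about 5%.
- If the score is equally correlated with the pre and post values, the change-score test rejects about 5% and ANCOVA about 3.5%.

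So the conservative test switches with an assumption that the documents do not address. These two figures illustrate the switch and are not general results. The power gain at r = 0.5 survives in both cases, at about 9 points (34.5% to 43.7%) and about 7 to 8 points (35.4% to 42.9%).

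**The case against.** The strongest reply is that group × time ANOVA is a standard, valid analysis that directly answers a question about greater change, so ANCOVA is a preference between two sound estimators. Part of this stands: nothing in the plan is wrong on this point. It does not remove the precision argument, because the covariate has already been measured and the groups are small.

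Three stronger readings are tempting, and the documents support none of them.
- **A reader might infer that ignoring the matched pairs makes the planned test invalid, or makes it the conservative one.** Step 3 shows that the direction depends on an unknown. Age, height and body mass barely move over 12 weeks, so an equal relation to pre and post values is at least as plausible as a relation through baseline only. Matching in Arm 2 also rests on the single word identical, while Table 1 lists different strength tests for that arm.
- **A reader might infer that pre and post values were analysed as if independent.** The SAP does not say whether the ANOVA has a subject term, but its use of paired t-tests post hoc points towards within-subject handling. Without a subject term, the group × time test would be strongly conservative (simulated rejection 0.7% at r = 0.5 and 0.1% at r = 0.7, N = 20, unmatched). The interaction test would still not produce excess false positives.
- **A reader might infer a large loss of power.** The gain shrinks quickly as r rises, and the effect of 0.75 SD is only an assumption.

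It is also fair to say that a second result for every primary outcome, after the data have been analysed, adds room for selective reporting. That stands, and the fix has to guard against it.

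**Conclusion.** This is a minor point of efficiency. No model adjusts for the baseline value. Provided that time is within subject, the planned interaction test is unbiased and keeps its error rate at or below 5%. Under the stated assumptions the forgone power is about 7 to 8 points at r = 0.5, 4 to 5 at 0.7, 2 at 0.8 and nil from about 0.9. The correlation, SD and effect size are not in the documents, so the actual loss is unknown and may differ between outcomes. The figures cover the 12 two-way analyses; no gain was computed for tendon area or rate of torque/force development. The missing pair term is a true description of the models, but it supports no general statement about which test is conservative or by how much.

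**What to change.** 1. For each two-way outcome, fit post value = group + baseline value of that outcome, and report the adjusted collagen-placebo difference with a 95% CI.
2. Keep the ANOVA as the planned result. Label the ANCOVA post hoc and show the two side by side for every outcome, whichever way each falls. Where they disagree, say that the conclusion depends on the model.
3. For tendon area and rate of torque/force development, a mixed model may be added: baseline at the same location or window, location or window, group, their interaction, and a participant random effect. It should use a small-sample df method such as Kenward-Roger.
4. Use the matched pair or the matching variables in sensitivity analyses only. In the change-score comparison, a pair term would cut error df from 18 to 9 with 10 pairs. Name the strength measure used for matching first: Table 1 offers two candidates in Arm 1 (knee extensor torque and squat) and one in Arm 2 (isometric force).
5. State whether the ANOVA treats time as within-subject.

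**Cost.** Revised SAP wording and a re-run on data already held. The downsides are one degree of freedom for the baseline covariate, no gain where r is about 0.9 or higher, a second result per outcome, and unavoidable post hoc status, since Table 1 dates the analyses to between January 2022 and September 2023.
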